b Total 24-hr urinary dapagliflozin excretion will also be measured at the end of each treatment period

c WOCBP must have a negative serum or urine pregnancy test result (minimum sensitivity 25 IU/L or equivalent units of HCG) within 0 to 72 hours before the first dose of study drug.

d Subject will be asked to collect 24 hour urine after informed consent is obtained. The subject will be requested to return the urine sample to the site on the following day.

e Specify details about specimen collection will be provided in the laboratory manual. Table 1-2 will list the laboratory assessment to be performed.

f Specify details about specimen collection, storage and processing will be provided in the laboratory manual.

g Visit 6 Serum or Urine Pregnancy Test is required for Canada sites per local regulatory requirement

Study Periods and Procedures:

Screening

Chronic Kidney Disease aged between 18 and 75 years, proteinuria levels between 500 and 3500 mg/24-hour, and an eGFR ≥ 25 ml/min/1.73m² who are on an ACEi or ARB, or can start with an ACEi or ARB, will be eligible for protocol-specific assessment during the screening period. Signature of the protocol-specific informed consent form constitutes the first procedure of the screening period, followed by the assignment of a unique subject number. Protocol-specific assessments and procedures may then be performed, as part of the screening visit, to evaluate the subject's eligibility. During the screening period, subjects will maintain their stable doses of commercially available ACEis or ARBs, and diuretic medication.

When all inclusion and exclusion criteria have been evaluated and the requirements for entry into the study have been met, the entry into run-in period or double blind treatment period will be scheduled. If the patient does not qualify based on the laboratory data, the patient is allowed to be re-screened within 3 weeks of the original screening date. The laboratory data based on which the patient failed should be repeated.

Run-in Period:

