Subjects will be followed for a total of 6 weeks on double-blind study medication in each active treatment period. A telephone visit will be scheduled after 1 week to assess tolerability. If the patient does not tolerate medication a visit to the out-patient clinic will be scheduled. The next scheduled visit (visit 4) occurs 3 weeks after randomization. A visit window of +/- 3 days is allowed for each out-patient clinic visit. Patients are asked to collect a 24-hr urine and blood will be sampled for clinical chemistry measurement. The last scheduled visit in the first treatment period is scheduled after 6 weeks. The last visit of the treatment period will include GFR measurement by plasma clearance of nonradioactive iohexol after a single venous dose, collection of a 24-hr urine sample and clinical chemistry measurements. At the end of the treatment period, the patient will take study medication *BEFORE* the GFR measurement procedure. In addition to using blood samples for GFR measurements, the samples will also be used to measure plasma concentration dapagliflozin and its metabolite dapagliflozin-3-O-glucuronide.

Visit 6,7,8, and 9

Following the last visit of the first treatment period subjects proceed to a 6 weeks wash-out period. After 6 weeks the second double blind treatment period will start. All visits and procedures in the second treatment period are similar to the first treatment period.

Visit 10

Six weeks after the second treatment period another visit will be scheduled. Procedures during this visit include GFR measurement with non-radioactive iohexol, 24-hr urine collection, blood pressure recording and blood sampling for clinical chemistry assessment.

Subjects who discontinue prematurely from the treatment period prior to visit 4, will have an abbreviated Week 12/ET visit, which will exclude measurements of GFR.

Clinical Lab Assessments

All protocol required local laboratory assessments, as defined in Table 1-2, must be conducted in accordance with the Laboratory Manual, and Time and Event Table.

Table 1

Plasma Laboratory Assessments		Parameters	
Hematology		Hemoglobin	Hematocrit
Clinical Chemistry	Urea	Bilirubin	
	Creatinine	Phosphate	
	AST	Calcium	
	ALT	Glucose	
	Total Protein		
Lipid Parameters	LDL	HDL	
Electrolytes	Sodium	Potassium	
	Chloride	Bicarbonate	
Other Laboratory Test	NT-proBNP ¹	HbA1C	
	Urine/Serum		
	Pregnancy Test ²		

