7.3 Study procedures

• Physical examination

Patients will be subjected to physical examination by the principal investigator or delegate as specified in Time and Event table. This physical examination entails a

routine investigation of heart, lungs, and abdomen. At each visit patients will be asked for adverse events related to urinary tract infections or genital infections.

- **24hr urine collection**

Patients are asked to collect 24hr urine at start and end of each treatment period to monitor albuminuria. In total, nine 24hr urines are collected during the course of this study. 24hr urine collection instructions will be provided to each patient. The volume of the urine containers is determined when the patient delivers the urine at each visit. Subsequently part of the urine is used for clinical chemistry measurement and the other part stored per instructions in the laboratory manual.

- **GFR measurements**

GFR measurements by plasma clearance of non-radioactive iohexol will be performed at the randomization and Week 6, 12, 18, 24 or early termination visits. This test involves a single dose injection of 5 mL of iohexol, a non-radioactive iodinated x-ray contrast agent. GFR is estimated on the basis of plasma disappearance curves.

The central laboratory of the UMCG will be providing detailed instructions for the GFR measurement procedure in a separate laboratory manual. The iohexol solution will be bought by the investigational site and should be used in accordance with the approved product label and manual instructions.

The following should be considered prior to performing GFR measurements:

- Subjects should be well hydrated prior to and following administration of iohexol.
- If not obtained within 72 hours of the GFR measurement procedure, the subject's weight and height should be measured and recorded

Subject preparation:

After a 10-hr fast, two intravenous (IV) catheters, one in each arm, will then be placed in the subject's antecubital vein. One line will be used for the single dose injection of nonradioactive iohexol. The second line will be used for intermittent blood sampling. At the beginning of each treatment period (i.e. visit 2 and 6), study medication will be taken **AFTER** the iohexol GFR measurement procedure. At the end of the treatment period (i.e. visit 5 and 9) study medication will be taken **BEFORE** the iohexol GFR measurement procedure.

Iohexol injection (time -2 to 0 minutes):

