At each of the visits, approximately 20 ml will be taken for routine blood tests (approximately 20 ml/ 9 visits = 180 ml). At each of the 5 visits to assess kidney function, approximately 24 ml will be taken (total 120 ml), plus another 20 ml at each kidney function visit for measurement of hormones and other factors associated with kidney disease (approximately 20 ml for each of the 5 kidney visits = 100 ml). At the end of each of the 2 treatment periods, 9 blood samples of 1ml will be taken for dapagliflozin PK analysis (total 18ml). A total of approximately 418 ml of blood will be collected over a 6 month (24 week) period

- Laboratory measurements

All routine laboratory measurements of this study will be assessed at the local laboratories of participating centres.

- Dapagliflozin plasma concentration measurement

At the end of the treatment period, during the GFR assessment, 9 blood samples of 1 ml will be drawn for dapagliflozin and its metabolite dapagliflozin-3O-glucuronide measurement.

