8.2.3 Adverse events of interest

Urinary tract infection or genital infections

All potential events of urinary tract infection or genital infections will be recorded in the eCRF.

Diabetic ketoacidosis (DKA)

All potential events of DKA will be recorded in the eCRF.

Volume depletion

Events of volume depletion (eg, dehydration, hypovolemia, or hypotension) will be collected on the eCRF as AEs.

Fractures

All fractures will be recorded in the eCRF as AEs.

Major hypoglycaemic event

A major hypoglycaemic event is defined as an event that requires assistance of another person to actively administer carbohydrates, glucagon, or take other corrective actions. Plasma glucose concentrations may not be available during an event, but neurological recovery following the corrective actions is considered sufficient evidence that the event was induced by a low plasma glucose concentration. Major hypoglycaemic episodes will be recorded in the eCRF as an AE.

Acute Kidney Injury

Acute kidney injury is defined as an increase of 40% in serum creatinine from the previous visit or hospitalization due to acute kidney injury. All acute kidney injury events will be recorded as an AE.

Amputation and related events:

Amputations and related events will be recorded in the eCRF. Information on the actual amputations will be captured as an AE.

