5.1. Analysis of primary outcome

The log-transformed 24-hour proteinuria values will be analyzed by a mixed-effects general linear regression model with treatment and period as fixed factor and patients (nested in sequence) as a random factor. This type of model, which accounts for repeated observations within individuals (measurement occasion at level one, individuals at level two) will allow us to estimate the treatment effect (estimated by restricted maximum likelihood). We will also explore the period-specific treatment effect adding in the model the interaction between the treatment and period covariates. If the baseline characteristics will be considerably different across the three regions included (Malaysia, North America, Europe) we shall consider to include region as a layer in the multilevel model fitted or as fixed effect covariate. We will also analyse the log-transformed 24-hour albuminuria values (a specific protein using the same model as described above).

The change in secondary outcomes, mGFR, eGFR, body weight and systolic blood pressure will be analyzed by the same model as showed for the proteinuria outcome.

In general, the models employed will be:

$$y_{it} = \beta_{0i} + \beta_1 Treat_{it} + \beta_2 Period_{it} + \beta_3 Interaction + \varepsilon_{it}$$

$$\beta_{0i} = \beta_0 + u_{0i}$$

$$\varepsilon_{it} \sim N(0, \sigma_\varepsilon^2)$$

Where y_{it} is the outcome for the individual i at time point t , β_{0i} is the intercept for individual i comprised of a sample-average fixed effect β_0 and an individual effect u_{0i} and ε_{it} is the residual error.

Complete case analyses, that is analysing records that present the whole set of information (outcome and covariates) for every visit of the patients will be performed. Patterns of missing data (for the outcomes and the covariates) will be reported. If the proportion of missing records is higher than 5% and/or we will suspect of particular missing mechanisms we will impute the missing values by multiple imputation using the full conditional specification.

Further, if there will be baseline measurements that are missing we will use the values measured at the screening visit: we will document the frequency of this imputation.

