As a complementary analysis we will also include week 3 (mid-period 1 visit) and week 15 (mid-period 2 visit) data points so to explore potential “immediate” treatment effects: this will be done for the primary outcome and the secondary outcomes for which the data is available (for instance, no eGFR is collected at week 3 and 15).

A fully-adjusted model will be also considered for the primary outcome including – among the others – the following time-varying variables: mGFR, systolic blood pressure, body weight and Hba1c.

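### The week 3/15 analysis in SAP 5.1 wrongly treats eGFR as not collected, and its model has no visit term with which to estimate an early effect

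*SAP*

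**What the plan says.** SAP 5.1 describes a complementary analysis that brings in the mid-period visits (weeks 3 and 15) to explore early treatment effects. It covers the primary outcome and whichever secondary outcomes have data at those visits. As its example of an outcome without data, it says that "no eGFR is collected at week 3 and 15".

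The same section makes eGFR a secondary outcome: "The change in secondary outcomes, mGFR, eGFR, body weight and systolic blood pressure will be analyzed by the same model". The model described has treatment and period as fixed factors and patient as a random factor, with two levels: "measurement occasion at level one, individuals at level two". The displayed equation, offered as the general form, adds one interaction (treatment by period) and independent residuals. No separate model is given for the week 3/15 analysis.

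For the week 3 visit, Protocol section 3 says: "Patients are asked to collect a 24-hr urine and blood will be sampled for clinical chemistry measurement". Procedures in the second period are described as similar.

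**The concern.** There are three linked problems.

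1. The SAP names an available secondary outcome as its example of missing data. An analyst who follows the remark omits eGFR at weeks 3 and 15, which is the only on-treatment GFR information before the end of each period.
2. The analysis is meant to explore an early effect, but the stated model has no term that separates week 3 from week 6. The hypothesis in both documents is of an acute fall in GFR and albuminuria, so the timing matters.
3. Once each period contributes two values, a patient-only random effect treats them as independent given the patient. If they share period-level variation, the confidence interval is too narrow.

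**Working it through.** **Is creatinine available at weeks 3 and 15?**

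- The Time and Events Table (Protocol section 3) marks blood sampling at V4 (week 3) and V8 (week 15).
- Footnote e to that row says "Table 1-2 will list the laboratory assessment to be performed", and Table 1 lists creatinine under clinical chemistry.
- Protocol 7.3 counts "approximately 20 ml will be taken for routine blood tests (approximately 20 ml/ 9 visits = 180 ml". The table marks V0, V1, V2, V4, V5, V6, V8, V9 and V10, which is nine only if V4 and V8 are included.
- Protocol 8.2.3 adds weaker support: "Acute kidney injury is defined as an increase of 40% in serum creatinine from the previous visit".
- Iohexol GFR, by contrast, "will be performed at the randomization and Week 6, 12, 18, 24 or early termination visits", so it is absent at weeks 3 and 15.

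The blood list in SAP 4.1 does not name creatinine at any visit, yet the SAP analyses eGFR. That list therefore cannot settle the question. On the protocol schedule, eGFR can be calculated at weeks 3 and 15 and mGFR cannot.

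**Planning inputs.** The documents give a reduction of 0.288 on the log scale (25%), an SD of 0.7 (within-subject 0.475), 50 completers and 80% power. A two-sided 5% paired t-test with 0.7 as the SD of the difference needs 49 patients and has 81.4% power at 50. Then 50/0.95 = 52.6, giving 53 enrolled. The plan's figures are reproduced. That reading implies 0.7/√2 = 0.495 per value, not 0.475. I use the stated 0.475; using 0.495 would make the standard errors about 4% larger and leave the error rates unchanged.

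**What the stated model estimates.** With complete data and two visits per period, the treatment coefficient is the equal-weight mean of the two visit effects, (d3 + d6)/2. The documents give no week 3 effect, so d3 is an assumed range with d6 = 0.288:

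| Week 3 effect (log) | Coefficient | Reduction, 1 − exp(−coefficient) |
|---|---|---|
| 0 | 0.144 | 13% |
| 0.144 | 0.216 | 19% |
| 0.288 | 0.288 | 25% |

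In a simulation of 200 trials per scenario (50 patients), the opposite patterns −0.144 then −0.288 and −0.288 then −0.144 both returned −0.217. Adding visit interactions recovered the week 3 effects as −0.141 and −0.283.

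**Standard error.** Let ρ be the share of the within-patient variance σ² that is common to the two values in a period. The documents do not give ρ.

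- True variance of the treatment estimate: σ²(1 + ρ)/50.
- Within a patient, the between-period mean square (1 df) has expectation σ²(1 + ρ) and the within-period mean square (2 df) has σ²(1 − ρ). The random-intercept model pools them to σ²(1 − ρ/3).
- Ratio of model SE to true SE: √[(1 − ρ/3)/(1 + ρ)].
- Approximate type I error: 2[1 − Φ(1.96 × ratio)].

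| ρ (assumed) | SE ratio | Type I, formula | Type I, simulated |
|---|---|---|---|
| 0 | 1.000 | 5.0% | 5.0% |
| 0.1 | 0.937 | 6.6% | 6.6% |
| 0.2 | 0.882 | 8.4% | 8.3% |
| 0.3 | 0.832 | 10.3% | 10.1% |
| 0.5 | 0.745 | 14.4% | 14.6% |

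The simulated column is from 40,000 null trials per row (25 patients per sequence). Simulated model SE against true SD was 0.067/0.068 at ρ = 0, 0.063/0.076 at 0.3 and 0.061/0.082 at 0.5. Testing on period means, which is equivalent to adding a patient-by-period effect, gave 4.8% to 5.1% throughout.

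If change from each period's own baseline is analysed, the two changes share that baseline. With independent residuals of equal variance, each change has variance 2σ² and their covariance is σ², so their correlation is 0.5. Simulated type I error was again 14.6%.

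**The case against.** **eGFR.** The operative rule is data availability, and the eGFR remark is only an example. If creatinine exists, the rule admits eGFR, and the remark may be a slip for mGFR. That is fair, and the slip is the likely explanation, although it is an inference. The remark still tells the analyst something the protocol contradicts, about an outcome the SAP itself lists.

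**The model.** The SAP does not expressly tie this analysis to the general equation, and the outcome is indexed by time point. SAP 5.3 refers to a longitudinal model with suitable contrasts, so visit terms may have been intended. But 5.3 says this only for the analysis after stopping drug. The treatment-effect shells (SAP Tables 6 and 7) have rows for overall, period 1 and period 2, and none for week 3. Weeks 3 and 15 appear only in the descriptive Tables 3 to 5 and, optionally, Figure 4. Those summaries keep the early data visible but do not supply the model-based crossover estimate.

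**Size.** If the full effect is present by week 3, as an acute mechanism might suggest, averaging loses nothing. That is true, but the stated model cannot show whether it is so.

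**Standard error.** The share is unknown, the primary model is for log values and not changes, and an exploratory analysis carries no confirmatory error claim. All of this stands. The change-from-baseline case is still relevant, because SAP 5.1 speaks of change in secondary outcomes and Tables 6 and 7 report change from baseline. The point remains conditional.

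**Conclusion.** The concern holds. The eGFR statement conflicts with the protocol schedule. The model as stated cannot separate an early effect from the end-of-period effect: for a 25% week 6 effect, it reports anything from 13% to 25% as the week 3 effect goes from none to all of it. These figures assume complete data and equal numbers per sequence.

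The interval problem is conditional: no understatement at a share of zero, and about 15% type I error at 0.5 or for change from own-period baseline.

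The scope is limited to an exploratory analysis. The iohexol GFR endpoint, the sample size and any analysis with one end-of-period value per period are not affected. It should be corrected, but it does not threaten the main result.

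**What to change.** In SAP 5.1, change eGFR to mGFR in the remark on weeks 3 and 15, and state that eGFR at those visits is analysed from the scheduled creatinine. For this analysis, add visit and treatment-by-visit fixed effects, and report the week 3/15 and week 6/18 effects separately. Add a patient-by-period random effect or an equivalent within-period covariance.

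The cost is SAP wording and a few model terms, with no new data. Each visit-specific effect is less precise than the average: SE = 0.475 × √(2/50) = 0.095, or a 95% interval of about ±0.19 log (a factor of 1.21), against an SE of 0.475 × √(1/50) = 0.067 for the average at share zero. Intervals for the averaged effect widen by the inverse of the SE ratio: 0% at share 0, 13% at 0.2, 20% at 0.3 and 34% at 0.5.

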5.2. Subgroup and sensitivity analyses

The primary and secondary outcomes will be analyzed in the following subgroups:

1. Age (\geq or $<$ 60 years or median)
2. Gender (Male / Female)
3. Region (Asia, Europe, North Am)
4. Proteinuria (\geq or $<$ 1000 mg/24hr)
5. mGFR (\geq or $<$ 45 ml/min/1.73m² or median)
6. Systolic blood pressure (\geq or $<$ 130 mmHg or median)
7. Body mass index (\geq or $<$ 25 kg/m² or median)
8. Kidney Diagnosis
9. Diuretic use (Yes/No)

We will flag patients who have started or changed the dose of any medication that may influence the primary outcome (e.g. NSAID, corticosteroids, diuretic treatment, mineralocorticoid receptor antagonists, and Vitamin D during the double blind treatment periods and perform a sensitivity analysis on the primary outcome excluding them.

Another sensitivity analysis will be performed on the primary outcome where we will use the average of the screening and randomization 24-hr proteinuria value.

All the analyses described in the SAP are based on the intention to treat principle (that is, patients analysed according to the group they were originally assigned). We will also perform the analyses on the primary outcome(s) considering “on treatment” patients defined as those with adherence to study medication \geq 80% (as determined by pill count).

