3.4 Sample size calculation

With a sample size of 50 patients completing the study and assuming a conservative standard deviation of 0.7 in log transformed proteinuria (within-subject standard deviation of 0.475), the trial will have 80% power to detect a mean reduction in albuminuria of 25% (i.e, $\delta=0.288$ on the log-transformed proteinuria scale) or more with dapagliflozin compared to placebo (alpha 0.05). This calculation is based on individual patient data from various clinical trials on the anti-proteinuric effects of different agents in diabetes and non-diabetes trials for which we have the individual patient data including ROAD, RENAAL and IDNT trials. For calculation of the sample size, the percent change in proteinuria is log-transformed to take into account the skewed distribution of proteinuria. Under the assumption that no carry-over effects and no period effects occur, a paired-t-

test is deemed appropriate to calculate the sample size. Using these assumptions, we calculate that 50 patients completing the study will provide 80% power to detect a 25% reduction in albuminuria. Assuming that approximately 5% of patients will discontinue the study prematurely, we intend to enrol 53 subjects.

We believe a reduction of >25% with dapagliflozin versus placebo can be detected. We recently published a large analysis of patients with diabetes and demonstrated that dapagliflozin decreased proteinuria by 33%. Trials with other SGLT2 inhibitors have also documented proteinuria reductions of approximately 30%.

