3.2. Sample Size

Sample size calculations estimated 50 patients completing the study would provide 80% power to detect a 25% reduction in albuminuria. Assuming that approximately 5% of patients will discontinue the study prematurely, we intend to enrol 53 subjects. This calculation assumed a conservative standard deviation of 0.7 in log transformed proteinuria (within-subject standard deviation of 0.475) in order to detect (with alpha at 0.05) at least the 25% reduction in mean albuminuria (i.e, delta=0.288 on the log-transformed proteinuria scale) in dapagliflozin compared to placebo.

4. Study population

Male and female subjects with Chronic Kidney Disease aged between 18 and 75 years, proteinuria levels between 500 and 3500 mg/24-hour, and an eGFR ≥ 25 mL/min/1.73m² will be enrolled. Patients with type 1 or type 2 diabetes, polycystic kidney disease, glomerulonephritis with flares (lupus or anti-neutrophil cytoplasmic antibodies (ANCA) associated vasculitis) or ongoing active renal inflammation will be excluded. Patients have to be treated with a stable dose of an ACEi or ARB for at least 4 weeks prior to enrolment.

The study population will be selected from the outpatient clinical from hospitals based in the Netherlands (Groningen, Almelo, Amsterdam), Canada, (Toronto, Calgary, Vancouver) and Malaysia (Kuala Lumpur) with the following pre-specified inclusion and exclusion criteria.

Inclusion criteria

- Age ≥ 18 and ≤ 75 years
- Diagnosis of IgA nephropathy, focal segmental glomerulosclerosis, or membranous nephropathy. A biopsy proven diagnosis is not a prerequisite for participation in this study.
- Urinary protein excretion > 300 mg/g and ≤ 3500 mg/g in a 24-hr urine collection
- eGFR ≥ 25 mL/min/1.73m²
- On a stable dose of an ACEi or ARB for at least 4 weeks prior to randomization
- Willing to sign informed consent
- Women of Child-Bearing Potential (WOCBP):
 - WOCBP must be using an acceptable method of contraception to avoid pregnancy throughout the study and for up to 4 weeks after the last dose of study drug in such a manner that the risk of pregnancy is minimized.
 - WOCBP must have a negative serum or urine pregnancy test result (minimum sensitivity 25 IU/L or equivalent units of HCG) within 0 to 72 hours before the first dose of study drug.
 - Women must not be breast-feeding.

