4.2. Randomization and blinding

Treatment sequence of dapagliflozin and placebo will be randomized. A computer generated randomized code generated by the sponsor will be used. The pharmacy of each participating centre will store the randomization code. Unblinding is not to be performed for any reason, other than an emergency where unblinding is required.

5. Statistical analysis

The flow of patients through the study (screened, fulfilled eligibility criteria, excluded, randomized and potential drop-outs) will be graphically displayed in a CONSORT diagram. Baseline characteristics will be described by sequence group. All tests are to be two-sided with nominal level alpha set at 5%.

Descriptive statistics will be used to analyse the means and distribution between all the study variables. The means of the normal distributed variables will be compared with the student T-test and non-parametric tests (Mann-Whitney U-test for continuous and Chi-Square test for categorical variables) will be used for the variables that present a particularly skewed distribution.

The base-case analyses of the treatment effects will be unadjusted (with the exception of the period effect).

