Change from baseline in period 2				
N Mean (SD)	xxx xxx xxx	xxx xxx xxx	xxx xxx xxx	xxx

Table 8: Treatment effect for primary outcome by pre-specified subgroups

Primary outcome	Dapa (N=xxx)	Placebo (N=xxx)	Difference (Dapa – Placebo) (N=xxx)	p-value
Change from baseline in overall				
Subgroup1				
Yes	xxx xxx xxx	xxx xxx xxx	xxx xxx xxx	xxx
No	xxx xxx xxx	xxx xxx xxx	xxx xxx xxx	xxx
Subgroup2				
Yes	xxx xxx xxx	xxx xxx xxx	xxx xxx xxx	xxx
No	xxx xxx xxx	xxx xxx xxx	xxx xxx xxx	xxx
Subgroup3				
Yes	xxx xxx xxx	xxx xxx xxx	xxx xxx xxx	xxx
No	xxx xxx xxx	xxx xxx xxx	xxx xxx xxx	xxx
Subgroup4				

Yes	XXX XXX XXX	XXX XXX XXX	XXX XXX XXX	XXX
No	XXX XXX XXX	XXX XXX XXX	XXX XXX XXX	XXX
Subgroup XXX				

Figure 1: Patients flow chart based on CONSORT

Figure 2: Primary outcome over time by treatment groups and periods. (

[figure not shown]

Figure 3: Bar charts with changes from baseline to week 6 for primary/secondary outcomes

Figure 4: Process measurements over time

Similar figure as above, but could add more time points in week 3 and week 15.

Figure 5: Forest plot for subgroup analysis for primary outcome

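### The SAP's subgroup analyses have no treatment-by-subgroup interaction test, the primary-outcome table gives a p-value per level, and four of nine factors leave the cut-point open, so a uniform effect can easily look uneven

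*SAP*

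**What the plan says.** SAP 5.2 says "The primary and secondary outcomes will be analyzed in the following subgroups" and lists age, gender, region, proteinuria, mGFR, systolic pressure, body mass index, kidney diagnosis and diuretic use. It names no test for a difference in effect between levels. The only interaction in the SAP is treatment by period, in 5.1.

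The layout appears in SAP section 7, in "Table 8: Treatment effect for primary outcome by pre-specified subgroups". Each level row has cells for dapagliflozin, placebo, their difference and a p-value. No row or column holds an interaction p-value. Figure 5 is a forest plot for the primary outcome. Section 7 has no subgroup shell for secondary outcomes.

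The age cut is given as "60 years or median". mGFR (45), systolic pressure (130) and BMI (25) have the same alternative. Proteinuria has a single cut, at 1000 mg/24hr.

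The opening of SAP section 5 says "All tests are to be two-sided with nominal level alpha set at 5" per cent. No multiplicity rule or exploratory label covers the subgroups. Protocol 9.1 to 9.3 plan no subgroup analysis, so the SAP is the only control on these comparisons.

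**The concern.** A p-value within a level tests whether the drug works in that level. It does not test whether the effect differs between levels. With about 50 completers, each level is underpowered, so one level reaching significance while the other does not is an ordinary result even when the effect is identical in both. Table 8 offers nothing else on which to judge a difference. The trial's rationale is a haemodynamic effect shared across varied non-diabetic kidney diseases, so a spurious split by kidney function, proteinuria or diagnosis would attract attention.

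The median alternative adds a second problem. For four factors the table calls the subgroups pre-specified, yet the cut can still be chosen after results are seen.

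**Working it through.** **Inputs.** The SAP (3.2) says that "50 patients completing the study would provide 80% power to detect a 25% reduction in albuminuria", with "delta=0.288 on the log-transformed proteinuria scale". Protocol 3.4 works by "assuming a conservative standard deviation of 0.7 in log transformed proteinuria (within-subject standard deviation of 0.475") and sizes the trial with a paired t-test. Alpha is 0.05 two-sided. Protocol 3.4 also cites a 33% reduction in patients with diabetes, which is −ln(0.67) = 0.400 on the log scale. The documents give no subgroup sizes, so the splits below are assumptions.

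**The plan's own figure.** Take 0.7 as the SD of the paired difference. At n = 50 the noncentrality is 0.288 / (0.7/√50) = 2.91, which gives 81.4% power; 80% needs 49 completers. With 5% dropout, 50/0.95 = 52.6, so 53 enrolled. The plan reproduces. The within-subject SD instead implies a difference SD of 0.475 × √2 = 0.672, giving 84.4% power at n = 50. It serves as a sensitivity value.

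**Apparent disagreement under a uniform effect.** Let p1 and p2 be the paired-t power in each level. The chance that exactly one is significant is p1(1 − p2) + p2(1 − p1).

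| Reduction | SD of difference | Split | Power per level | Exactly one significant |
|---|---|---|---|---|
| 25% | 0.7 | 25/25 | 0.506, 0.506 | 50.0% |
| 25% | 0.7 | 35/15 | 0.657, 0.318 | 55.7% |
| 25% | 0.7 | 40/10 | 0.718, 0.214 | 62.5% |
| 25% | 0.672 | 25/25 | 0.539, 0.539 | 49.7% |
| 33% | 0.7 | 25/25 | 0.784, 0.784 | 33.9% |
| 33% | 0.672 | 25/25 | 0.816, 0.816 | 30.0% |
| 33% | 0.7 | 40/10 | 0.942, 0.366 | 61.8% |

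First row: 2 × 0.506 × 0.494 = 0.500. Second row: 0.657 × 0.682 + 0.318 × 0.343 = 0.557.

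**Several factors together.** Seven of the nine factors have two levels. A simulation of 20,000 trials with seven independent 25/25 factors on the same 50 patients found at least one disagreement in 87% of trials for a 25% effect and 67% for a 33% effect. Correlated factors would lower these figures somewhat.

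**The interaction test.** This is a two-sample t-test on the paired differences. Its false-positive rate is 5% per factor. For at least one of seven independent tests it is 1 − 0.95^7 = 30%, and for nine it is 1 − 0.95^9 = 37%. At 25/25 the standard error of the between-level difference is 0.7 × √(1/25 + 1/25) = 0.198. Power is about 30% for a between-level difference of 0.288 and 81% for 0.576.

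**The open cut-point.** If the more favourable of the median and a fixed cut is used, with the fixed cut assumed to lie between the 30th and 70th percentiles, simulation puts the interaction test's false-positive rate at about 7 to 9% instead of 5%.

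**The case against.** The text of SAP 5.2 names no per-level p-value and gives no rule for reading one. The p-values come from a table shell with generic placeholder rows, in a section headed as proposals, so part of this is silence on method. That is fair, but the shell is the only statement of how the subgroups will be reported. Where the authors wanted an interaction, for treatment by period, they wrote one.

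Several stronger readings are tempting and are not supported:

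- A reader might multiply about 20 levels by five outcomes to get about 100 p-values, with about 5 false positives under no effect. Table 8 covers the primary outcome only. The count of 20 assumes about three diagnosis levels, which SAP 5.2 does not define. A count under no effect also does not measure how often a real, uniform effect looks uneven.
- A reader might infer that the sponsor intends to treat unlike p-values as effect modification. Nothing says so. Subgroup effects are not a stated objective, and the forest plot helps a careful reader.
- A reader might take 50% as the rate. It belongs to the design effect with equal halves, where power per level is close to one half. Protocol 3.4 expects a reduction above 25%, and at 33% with equal halves the figure is 30 to 34%.

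Two further objections stand. The interaction test is weak at this sample size. Confidence intervals will also still show one level excluding zero and another not. Both favour cautious presentation; neither makes per-level p-values a test of difference.

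**Conclusion.** The point holds for the primary-outcome subgroup table and for the four factors with an open cut. Under a uniform effect, disagreement between two levels is expected in roughly 30 to 34% of trials (33% reduction) to 50% (25% reduction) at an even split, and in about 62% at 40/10. These figures rest on 50 completers, a difference SD of 0.7 (0.672 for the 30% figure), paired-t power and assumed splits. The cut-point choice is a smaller problem, affecting four of nine factors. For secondary outcomes, SAP 5.2 plans subgroup analyses but shows no table, so only the absence of an interaction test can be said of them. A reader might infer that the main result is at risk. It is not: the primary analysis and sample size do not depend on the subgroups. This is a cheap improvement to secondary interpretation.

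**What to change.** In SAP 5.2 and Table 8:

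- Add a treatment-by-subgroup term to the 5.1 mixed model, with the factor's week-0 value used for both periods. This also settles which baseline defines a subgroup, since Table 2 tabulates baselines for each period.
- Report one interaction p-value per factor, with level-specific estimates and 95% confidence intervals in place of level-specific p-values. Do the same in any secondary-outcome subgroup tables.
- Before unblinding, keep the cuts already written (60 years, 45 mL/min/1.73m², 130 mmHg, 25 kg/m²), delete the median alternative, and define the kidney-diagnosis levels.
- Label the subgroup analyses exploratory, and state the interaction test's low power and that the nine tests are unadjusted.

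The cost is SAP wording, one model term per factor and a revised table shell; no new data are needed. Fixed cuts may give uneven groups. The test will miss moderate differences, and a false signal in at least one of nine factors remains possible at the rate shown above, which is why the exploratory label matters.
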